Patients with CF, carrying 2 severe mutations referred to Class I and II, i.e. mutations associated with more severe LA deficiency and more severe clinical symptoms, (like delF508, 394delTT) are included after informed consent. The reason for including only those with clinically more severe phenotype is that those have pancreatic insufficiency and also other symptoms more expressively related to genotype (see above). Exclusion criteria will be pregnancy and transplantation and age above 15 and below 5 years (due to pulmonary function tests) and severe liver disease (cirrhosis, portal hypertension). The patients shall not have taken any lipid supplements for 2 months before inclusion and not be treated with any modulators (like Orkambi, Trikafta).

The patients will keep to their ordinary treatment of PERT and vitamins and that for the pulmonary symptoms and infections. No special dietary recommendations will be given, but PERT might be increased, when the supplement is given and that shall be registered. Number of pulmonary exacerbations and type of treatment, including antibiotics, are registered and also compared with the year before the study.

Sample size

A sample of 84 patients (42 per group) will ensure that a two-sided test with α =0.05 has 80% power to detect a 0.5 mean difference in 1-year change in weight-

for-age Z-score, assuming a pooled standard deviation of 0.8. This last figure has been obtained from a previous intervention study on cystic fibrosis patients (Alicandro et al. 2013). Since we expect a withdrawal rate of close to 10%, we planned to enroll 90 patients (45 per groups). The patients and caregivers will be informed by oral and written information and included after informed consent. The study is approved by local Ethic Committees and by the one at Karolinska Institutet and the study is performed according to the Helsinki Declaration.

Design

The study is designed as a double-blind randomized clinical trial

The patients will be randomized to either

- treatment A: linoleic acid (12 g for children 5-15 years) + 600 mg algeal DHA
- treatment B: oleic acid (12 g for children 5-15 years) + 600 mg algeal DHA

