The fatty acids will be given daily for 12 months, in vials containing an emulsion of totally 20 ml (provided by AKK Company, Karlshamn, Sweden and Copenhagen Denmark, packed by WinterMedic, Odense, Denmark), which can be mixed with milk, juice, sour cream, porridge or any similar feeding at breakfast time. Some extra enzymes may be added.

The treatment will last 12 months, starting and ending at time of the yearly check up of the patients. Half the number of patients will be randomly allocated to receive either treatment A or B. An independent researcher (not involved in the study) will generate the allocation sequence at each center. This will reduce small differences in local treatment policy. The vials with supplementation will only be coded (black or white capsula) so neither patient nor caregivers or staff in charge will be informed by the type of supplementation.

Primary Outcome

- BMI Z-score, weight-Z-score

Secondary outcomes

- Height Z-score
- FEV1 (% of predicted) and oxygen saturation
- Exacerbations and infectious parameters compared to year before.
- Plasma phospholipid fatty acid profile.
- Plasma concentration of IGF-I

Explanatory outcomes

- Bone mineral density
- Lean body mass and fat mass.
- Liver function tests
- Lipid mediators (like eicosanoids and docosanoids)
- Cytokines
- 8-iso-prostane
- Sweat sodium and chloride concentrations
- Renal sodium excretion
- Resting energy expenditure
- Intestinal function (fecal calprotectin and fat absorption coefficient)
- Oral glucose tolerance with insulin determination.

METHODS

Patients will be screened for enrollment and will be allocated to one of the treatment at baseline visit. Follow-up visits will be scheduled at 6 and 12 months after treatment allocation. Some measures, like fat absorption coefficient and calprotectin and resting energy expenditure, exhaled NO and ergometer test will not be performed in all patients due to limited capacity at some centres. The study procedures are summarized in table 1.

Table 1. Outline of study procedures

	Baseline visit: Screening and allocation	+6 months	+12 months
Anthropometry	X	X	X
DXA	X		X
FFQ	X	X	X
24-h dietary recall	X	X	X
Pulmonary function	X		X
Blood sample	X	X	X
F-Calprotectin	X		X
Urine sample	X		X
Ergometer test with oxygen saturation	X		X
Oral glucose tolerance	X		X
Indirect calorimetry	X		X
Sweat test	X		X
Compliance to treatment	X	X	X
CF Questionnaire	X	X	X

1. *Anthropometry.*

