Sampling. Mixture in local laboratory with freezing of an aliquote for later transport to Poznan

6. *Metabolic tests*

- Urine sample for 8-isoprostanate and lipid mediators as eicosanoids, docosanoids and linoleic acid metabolites (directly to freezer -80 each sample in 2 x 8 ml and in 4 x 2 ml) for later analyses in Stockholm.
- Indirect calorimetry at start and after 12 months (if available in the hospital).
- Sweat test at start and after 12 months. **Both sodium** and chloride analyses.
- Oral glucose tolerance test.

7. *Quality of life.*

Quality of life will be assessed through the CF Questionnaire Revised (CFQ), a disease-specific tool that measures health-related quality of life in patients with

CF. There are different versions of the questionnaire: two for children over 6 years, one to be completed by the child and one to be completed by parent (CFQ Child and CFQ-Parent, respectively).

8. Compliance with the treatment

Compliance with the treatment will be evaluated by monthly contact with the study coordinator of respective centre, when not used vials will be registered and new supplied. The patients are asked to make a dairy over the daily intake also reported monthly to the coordinator. Extent of physical activity shall be notified.

9. Statistics

All data will be collected in identical Excel files and analysed in one center at end study.

The main analysis will be carried out on the intention-to-treat population defined as all randomized patients. We will also conduct a secondary analysis on the per-protocol population excluding patients not receiving the allocated treatment for more than 2 months.

Between-treatment differences in the primary outcome across time points will be evaluated by fitting random intercept linear mixed-effects models. Mixed effects model can account for intra-correlated repeated measures on the same subjects and accommodate missing data due to dropouts. The models will include the z-score of BMI as response variable, treatment, time and time x treatment interaction as independent variables. The model coefficients for the time x treatment interaction will be considered an estimate of the treatment effect on changes in the study outcome. Time will be included in the model as categorical variable with the following categories: baseline (pre-treatment), +6 months and +12 months from treatment allocation.

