## 9. Statistics

All data will be collected in identical Excel files and analysed in one center at end study.

The main analysis will be carried out on the intention-to-treat population defined as all randomized patients. We will also conduct a secondary analysis on the per-protocol population excluding patients not receiving the allocated treatment for more than 2 months.

Between-treatment differences in the primary outcome across time points will be evaluated by fitting random intercept linear mixed-effects models. Mixed effects model can account for intra-correlated repeated measures on the same subjects and accommodate missing data due to dropouts. The models will include the z-score of BMI as response variable, treatment, time and time x treatment interaction as independent variables. The model coefficients for the time x treatment interaction will be considered an estimate of the treatment effect on changes in the study outcome. Time will be included in the model as categorical variable with the following categories: baseline (pre-treatment), +6 months and +12 months from treatment allocation.

Secondary and explanatory outcomes will be compared across treatment groups using the paired t-test for normally distributed variables, otherwise the non-parametric Wilcoxon signed-rank test for dependent samples will be used.

A stratified analysis by sex will be performed.

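### Allocation is generated by centre but the primary model has no centre-by-time term, so the analysis does not reflect the allocation; the likely cost is a small loss of precision, not bias

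*Protocol*

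**What the plan says.** - **Allocation (Protocol, Design).** An independent researcher "will generate the allocation sequence at each center. This will reduce small differences in local treatment policy". The ratio is 1:1: "Half the number of patients will be randomly allocated to receive either treatment A or B". Blocking is not mentioned and the number of centres is not given.
- **Primary model (Protocol, Methods, 9. Statistics; same words in SAP, 9. Statistics).** "The models will include the z-score of BMI as response variable, treatment, time and time x treatment interaction as independent variables". The model has a random intercept, and its purpose is repeated measures within a patient: "Mixed effects model can account for intra-correlated repeated measures on the same subjects and accommodate missing data due to dropouts". The treatment effect is read from the time × treatment coefficients. No centre term appears, fixed or random, and the only stratified analysis named is by sex.
- **Background care (Protocol, Patients and Eligibility).** Enzyme, vitamin, pulmonary and infection treatment continues as usual. No special dietary advice is given, and enzyme dosing may be increased and recorded.
- **Sample size (Protocol).** The calculation is for a "two-sided test with α =0.05 has 80% power to detect a 0.5 mean difference in 1-year change in weight" (continuing) "for-age Z-score, assuming a pooled standard deviation of 0.8". It has no centre component.

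**The concern.** The sponsor names local policy as a source of variation and randomises by centre for that reason, but the analysis then ignores centre. Background care is left to each centre, so children at different centres could plausibly gain weight at different rates over the year. When a design balances a factor that predicts the outcome and the model omits it, the model-based standard error does not match the true variability of the estimate. At stake are some precision and a correctly sized test. Silence on centre also leaves room for a choice about centre adjustment after the data are seen.

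**Working it through.** **1. The plan's own figure.** Inputs from the Protocol's Sample size section: difference 0.5, SD 0.8, two-sided α 0.05, power 80%.

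Normal approximation: n per arm = 2 × (1.960 + 0.842)² × 0.8² / 0.5² = 40.2, so 41 per arm (82 in all). With the noncentral t, power is 79.8% at 41 per arm and 80.8% at 42. This reproduces the stated figure, "A sample of 84 patients (42 per group"). It does not depend on a centre term.

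**2. Which centre differences matter.** With complete data, the time × treatment coefficient at 12 months is the between-arm difference in mean within-patient change. Anything constant over time for a patient cancels. The planned model was simulated with 6 centres of 14 (assumed), balanced within centre, 40 runs per scenario. Mean SE of the coefficient:

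| Centres differ in | No centre term | Centre main effect | Centre × time |
|---|---|---|---|
| level only | 0.1538 | 0.1538 | 0.1536 |
| change only | 0.1564 | 0.1564 | 0.1525 |
| both | 0.1617 | 0.1617 | 0.1547 |

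A main effect changes nothing. Centre × time lowers the SE only where centres differ in change.

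**3. Size under the planned three-visit model.** Let f be the share of the variance of 12-month change (0.8² = 0.64) that lies between centres. The documents do not give f; 10% and 20% are assumed. Assume also that the centre effect grows linearly over the year, that data are complete, and that there are 42 per arm.

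- Reference SE: 0.8 × √(2/42) = 0.1746.
- Arms balanced within centre: the true variance of a change is 0.64(1 − f), so the actual SE is 0.1746√(1 − f).
- Planned model: one residual variance is pooled over three visits. A centre effect of 0, ½c, c deviates from its mean by −½c, 0, ½c. The sum of squares is ½c² on 2 degrees of freedom, or ¼c². In the variance of a change this counts twice, as ½c². The model therefore uses 0.64(1 − f) + ½ × 0.64f = 0.64(1 − f/2), and its SE is 0.1746√(1 − f/2).
- SE ratio k = √[(1 − f/2)/(1 − f)].
- Type I error = 2[1 − Φ(1.96k)].
- Power without centre = Φ[(0.5 − 1.96 × model SE)/actual SE].
- Power with centre × time = Φ[0.5/actual SE − 1.96].

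| f | Model SE | Actual SE | k | Type I error | Power without | Power with |
|---|---|---|---|---|---|---|
| 0.10 | 0.1702 | 0.1656 | 1.027 | 4.4% | 84.3% | 85.5% |
| 0.20 | 0.1656 | 0.1561 | 1.061 | 3.8% | 86.9% | 89.3% |

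Simulation of the planned model (6 centres of 14, balanced within centre) agrees. At f = 0.10, power is 84.0% without and 85.1% with centre × time, and unadjusted type I error is 4.6%. At f = 0.20 the figures are 86.2%, 88.4% and 3.7%.

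**4. If sequences are not blocked.** Centre differences then also enter the true variance, which is close to 0.64, while the model still uses 0.64(1 − f/2). Type I error = 2[1 − Φ(1.96√(1 − f/2))] = 5.6% at f = 0.10 and 6.3% at f = 0.20. Simulation with simple randomisation within centre gave the same two values.

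**5. What the remedy can cost.** With 14 centres of 6, no blocking and fixed centre × time terms, simulated power fell from 81% to 73% at f = 0 and from 82% to 78% at f = 0.10.

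**The case against.** Four arguments on the other side have force.

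- **The design already does its job.** The stated purpose is that local policy should not differ between arms, and allocation by centre serves it under any model. This stands. A reader might infer that the benefit of allocating by centre is lost or that the estimate is biased; the documents support neither. Nor do all centre differences stay in the error, since stable differences in level go into the random intercept.
- **A conservative test presupposes balance within centre.** The documents do not state blocking, and without it the direction reverses (step 4). This stands, so the direction of the error cannot be asserted from the documents.
- **The effect is small, and no planned power is lost.** This stands. A reader might analyse 12-month change alone, where the SE ratio is 1/√(1 − f): 5.4% too large at f = 0.10 and 11.8% at f = 0.20, with about 2.5 and 5 points of power lost (83.0% vs 85.5%; 84.4% vs 89.3%). That is not the planned model, in which the inflation is about half. In both cases power without a centre term stays above the planned 80%, because 0.8 is a pooled SD and the sample size assumed no adjustment. What is given up is extra precision.
- **Fixed centre × time terms can do harm.** With many small unblocked centres they cost more than they return (step 5). This stands against unrestricted fixed effects, but not against a random term or adequate pooling.

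None of this removes the mismatch: the sponsor randomises by a factor that it considers relevant, and the plan does not say how the analysis will treat it.

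**Conclusion.** The point holds as one of precision and pre-specification. The primary analysis omits the factor by which allocation is generated. Only centre differences in change over the year are affected. With an assumed centre share of 10–20% and arms balanced within centre, the cost is about 1–2 points of power, with type I error of about 4.6% to 3.7%. Without blocking, the unadjusted test runs at or slightly above 5%. If centres do not differ in change, nothing is lost.

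These sizes rest on assumptions that the documents cannot confirm: the centre share, six equal centres, linear growth of the centre effect and complete data. They also carry over the SD of 0.8, which the Protocol gives for weight-for-age Z-score, to a model for BMI Z-score. Severity: minor to moderate.

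**What to change.** - **Model.** In section 9 of both documents, add centre × time (with the centre main effect) to the primary mixed model. A centre main effect alone leaves the time × treatment estimate exactly unchanged in complete balanced data; with dropout it could shift slightly.
- **Form of the term.** Use a random centre-by-time effect. Alternatively, use fixed effects with small centres pooled, for example by country or region, under a rule set before unblinding and tied to the number and size of centres.
- **Design section.** State the number of centres and whether the sequences are blocked, since both decide which form is sensible.

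**Cost.** A few sentences of text and no new data, because centre is known for every patient. The statistical price is a few degrees of freedom. With many small unblocked centres and fixed terms there is also a loss of power, which the random term or the pooling rule is meant to limit.

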Height and weight are controlled with the same equipment for each patient at respective centre and at each scheduled visit (baseline, 6 and 12 months after allocation). Z-scores of weight, height and BMI will be computed using WHO as growth standard. DXA is performed at start and after 12 months period for determination of bone mineral content and density, lean body mass and fat mass.

1. *Food registration.*

- Food frequency questionnaire (FFQ) will be performed at start and each scheduled visit, mainly used for calculation of energy intake and intake of fat and fatty acids (validated questionnaire Eriksson S et al. 2010). Since the products are different in different countries the FFQ form can only suggest **type** of products to be evaluated, complemented by the local dietician. The reason to include these registrations is to individually make a comparison with intake at start and end of study possible, checking that not major changes have occurred in diet, which can influence the results.
- 24-hour recall will be performed at start, 6 months and 12 months after allocation as a complement to FFQ for portion size, type of products etc.

3. *Pulmonary function.*

- Routine pulmonary function (FEV1) at each clinical visit
- Full spirometry at start and end of treatment
- Exhaled NO (if available)
- Ergometer test at start and end
- Oxygen saturation (ear-tip).

4. *Biochemistry.*

- Routine blood biochemistry (fasting) at start and end of treatment period, including Hb, platelets, white blood cell count and differential count, ASAT, ALAT, alkaline phosphatase, GGT, PK, total and conjugated bilirubin, bile acids, cholesterol, lipoproteins, triglycerides, urea, creatinine, glomerulus filtration rate. Ig-G, CRP, sedimentation rate.

- 1 ml serum/plasma for later analyses (to freezer divided in 4 tubes for later analyses of lipid mediators at KI).
- 0,5 ml for IGF-I analysis (to freezer for later analysis in Sweden)
- 0.5 ml plasma for cytokines (to freezer for sending to Stockholm for analyses (OLINK, Uppsala, Sweden).
- 0.5 ml plasma for analyses of phospholipid fatty acids (to freezer for later analysis in Poznan or Stockholm).
- Urine sample for routine tests, incl sodium and creatinine concentrations.

5. *Intestinal function*

- F-Calprotectin at start and after 12 months (in freezer for later analyses at one center)
- Fat absorption at start and 12 months. Three day dietary recording and feces

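### Treatment is masked only by a two-value cap code, so one decoding event can reveal the arm of every child whose cap colour the decoder knows

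*Protocol*

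**What the plan says.** The Design section of the protocol states: "The study is designed as a double-blind randomized clinical trial". The arms are "treatment A: linoleic acid (12 g for children 5-15 years) + 600 mg algeal DHA" and "treatment B: oleic acid (12 g for children 5-15 years) + 600 mg algeal DHA". Allocation is equal: "Half the number of patients will be randomly allocated to receive either treatment A or B". A researcher outside the study draws up the sequence centre by centre, and one contract company packs the vials.

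Masking is covered in one sentence: "The vials with supplementation will only be coded (black or white capsula" (the bracket closes there), "so neither patient nor caregivers or staff in charge will be informed by the type of supplementation".

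Under Compliance with the treatment (item 8), each centre's coordinator is in monthly contact with the families, "when not used vials will be registered and new supplied". Under Biochemistry (item 4), the plan is "0.5 ml plasma for analyses of phospholipid fatty acids (to freezer for later analysis in Poznan or Stockholm", again with the bracket closing there.

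Neither document mentions numbered kits, more than one code per arm, a colour key that differs by centre, a named key-holder or a way to break the code for one child. The SAP says nothing about blinding.

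**The concern.** A code with one value per arm puts everyone who handles vials one fact away from knowing many assignments. Even before any decoding, the cap sorts a centre's children into two treatment groups. Treatment begins and ends at each child's annual check-up, so start dates are probably staggered. Staff could then compare finished children by cap colour while others are still being treated.

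Decoding would not be neutral. The opening summary of the protocol expects linoleic acid to help, and the Background links high oleic acid to growth of *Staphylococcus aureus*. Someone who knew the colours would hold expectations that favour one arm.

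Several things that expectation can move are left to judgement during the year: enzyme increases, diet (for which no special advice is given), and the recognition and treatment of exacerbations. Exacerbations are a secondary outcome. The CF questionnaire is completed by children and parents. Weighing a child is objective, but what happens to the child between weighings is less so.

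**Working it through.** **Inputs**

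- Arms: 2 (Protocol, Design).
- Codes: 2, black or white (Protocol, Design).
- Enrolment: 90, or 45 per group (Protocol, Sample size).
- Number of centres, C: not given, so C is varied as an assumption, with centres of equal size.
- Whether one colour key serves all centres: not stated, so both cases are shown.

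**The plan's own figure.** The sample size reproduces. A two-sample t-test with difference 0.5, SD 0.8, two-sided α of 0.05 and 80% power needs 41.17 per group, which rounds up to 42, or 84 in total. Enrolment of 90 is taken as stated. This confirms the input and has no other bearing on the point.

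**Step 1: one key for the whole trial.** With two codes and two arms, learning what one colour means settles the other by elimination: 45 + 45 = 90 children, or 90/90 = 100%. This counts children whose arm could be read off by someone who knows both the key and every child's colour.

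**Step 2: a separate key at each centre.** One decoding event settles one centre, about 90/C children: 90/2 = 45, 90/3 = 30, 90/5 = 18.

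**Step 3: one key, but a local decoder.** A coordinator who knows only the local children's colours can also read off only about 90/C, unless the meaning of the colours is passed on.

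**Step 4: the alternatives.**

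| Coding | Children revealed by one decoding event |
|---|---|
| Two colours, one key, all colours known | 90 of 90 (100%) |
| Two colours, separate keys or a local decoder, C = 3 | about 30 |
| Two colours, separate keys or a local decoder, C = 5 | about 18 |
| Four neutral codes per arm, eight in all | 90/8 = 11.25, about 11 (12.5%) |
| Unique number per child | 1 of 90 (1.1%) |

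These figures count exposed assignments. They do not measure bias. Turning them into a shift in Z-score would need the chance of a decoding event and the effect of knowledge on behaviour, and the documents give neither.

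**The case against.** The strongest reply is that this is a fragile arrangement and not a demonstrated break in the blind. That is right, and it rules out several stronger readings that a reader might infer.

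- **That one slip certainly unblinds all 90 children.** This needs one trial-wide key and someone who knows every child's colour. A single packer and a single sentence for the whole trial make a shared key the plain reading, but the protocol does not say so, and vials are handled centre by centre. Ninety is the upper bound.
- **That the products themselves differ in colour.** The text appears to describe the cap. Nothing says that the emulsions look different.
- **That fatty acid profiles will reveal the arms during follow-up.** Samples are frozen for later analysis, and the Statistics section has the data analysed in one place at the end. This weakens the route without closing it, because no text bars release of results to centres.
- **That families comparing taste would break the code.** Taste could show that two products differ, but not which is linoleic acid. Whether the emulsions are matched is a separate question that kit numbers would not solve.
- **That later allocations become predictable.** Seeing colours balance within a centre helps only under restricted randomisation, such as blocking. The method is not described, so this cannot be concluded.

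It can also be said that the primary outcomes are measured objectively with the same equipment for each child, that both arms receive an active supplement, and that enzyme changes, exacerbations, antibiotics and diet are recorded. The CF questionnaire is scheduled at all three visits but is not in the outcome lists. These points limit the consequence. Recording helps to detect a drift between arms but does not prevent it.

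What stands is that a code-break cannot be confined to one child under the scheme as written.

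**Conclusion.** The point holds in a limited form. The stated masking uses one visible value per arm, so children who share a treatment can be recognised, and one decoding event reaches every child whose cap colour the decoder knows. The exposure is up to 90 children with a shared key and full knowledge of colours, or about 90/C with centre-specific keys or a local decoder, against 1 with individual numbers. The 90/C figures assume equal centres, and C itself is an assumption.

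The double-blind claim is weakened mainly for the outcomes and co-interventions that expectation can influence. The effect on the primary Z-scores cannot be derived in size or shown to exist. This is an inexpensive improvement that should be made, and not evidence that the blind will fail.

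**What to change.** Have the packer put identical caps on all vials and label each child's supply with a unique kit number from the independent researcher's list. State in the protocol that only the packer and that researcher hold the key linking kits to treatment. If the coloured caps have already been made, use several neutral codes per arm, spread across centres.

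Add a sentence that plasma fatty acid results are neither released to centres nor linked to treatment codes before database lock.

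The cost is label printing, preparation of a kit list and a short protocol edit, using a packer and an independent researcher who are already in place. The drawback is less flexible monthly resupply, because a child's new vials must carry that child's number. No extra visits or procedures are needed.

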Secondary and explanatory outcomes will be compared across treatment groups using the paired t-test for normally distributed variables, otherwise the non-parametric Wilcoxon signed-rank test for dependent samples will be used.

A stratified analysis by sex will be performed.

RISK-BENEFIT

There will be no adverse effects to expect of this treatment , since the control group will have the same treatment as offered generally to patients, i.e. extra calories. The extra LA will not exceed the general intake in US (Choque et al 2014). Both groups get similar amount of omega-3 fatty acids; dose in agreement with general recommendations. The extra burden of investigations is small since the patients always have more extensive investigations at the yearly checkup.

IMPORTANCE

If clinical status is improved the patients in both groups will be asked for the possibility to continue with Group A therapy for one further year (requires new ethical applications). Furthermore, good result would indicate a multicenter study for treatment from diagnosis in countries with neonatal screening, which would be extremely important since many of the symptoms start early and especially the supply of high caloric diet gives many problems in patients and parents, and unsatisfying results, It can also have the potential to be a cheap complement to modern expensive drug treatment.

A special benefit for individuals and society would be if this simple, cheap and non hazardous treatment can reduce the enormous costs of the modern drug treatment, which is further not always available.

References:

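### The exacerbation outcome is framed against the previous year and only tests for dependent samples are named, so the analysis as written tests change within patients rather than LA against OA

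*Protocol*

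**What the plan says.** - Protocol, Secondary outcomes: "Exacerbations and infectious parameters compared to year before". No other outcome in the lists is given a historical comparator.
- Protocol, Patients and Eligibility: "Number of pulmonary exacerbations and type of treatment, including antibiotics, are registered and also compared with the year before the study".
- Protocol, section 9 (Statistics): "Secondary and explanatory outcomes will be compared across treatment groups using the paired t-test for normally distributed variables". The SAP repeats this and gives the alternative for non-normal data: "otherwise the non-parametric Wilcoxon signed-rank test for dependent samples will be used".
- Protocol, Design: "The study is designed as a double-blind randomized clinical trial", with 1:1 allocation, so a concurrent randomised control is available.

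The mixed model in section 9 is specified for BMI Z-score only. Neither document names a count or rate model, gives the prior-year count a role as covariate, defines an exacerbation, or says how the prior-year count will be obtained.

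**The concern.** The LA and OA children are independent samples, so a test for dependent samples cannot compare them. The only natural pairing for this outcome is a child's own two years, and the outcome line points to exactly that pairing. The analysis would then ask whether children had fewer exacerbations than the year before, not whether LA did better than OA.

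The Protocol itself gives reasons to expect a change shared by both arms. Both receive the same algal DHA, which the Background suggests may help chronic airway inflammation. Both receive the same quantity of added fat, and the Risk-Benefit section describes the control as extra calories. Pancreatic enzymes may be raised during supplementation. Trial participation could add to this, as could closer counting in the trial year. A shared fall could be read as an LA effect, and a shared rise in recorded events could hide a real one. Randomisation removes both problems, but only if the arms are compared with each other.

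**Working it through.** **The plan's own figure.** The only sample-size figure concerns weight-for-age Z-score: difference 0.5, SD 0.8, two-sided 5%, 80% power. n = 2 × (1.960 + 0.842)² × 0.8² / 0.5² = 40.2, so 41 per arm by the normal approximation. The t-based solution is 41.17, rounded up to the stated 42. It reproduces, but says nothing about exacerbations.

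**Assumptions, because the documents give no rates.** Counts are Poisson with a gamma patient effect (mean 1, variance k) shared by a child's two years. The mean is μ = 1 or 2 per year, k = 0.5 or 1.0, with 42 per arm and no withdrawals. In the trial year, rates in both arms are multiplied by a common ratio c.

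**1. Within-arm test, no LA effect.** The expected within-child change is −μ(1−c), with variance μ(1+c) + μ²(1−c)²k. By normal approximation with n = 42 and k = 0.5:
- μ = 1, c = 0.8: variance 1.82, SE = √(1.82/42) = 0.208, z = 0.20/0.208 = 0.96, rejection about 16% (simulated 15.6%).
- μ = 1, c = 0.7: variance 1.745, SE 0.204, z = 1.47, about 31% (simulated 29.5%).
- μ = 2, c = 0.8: variance 3.68, SE 0.296, z = 1.35, about 27% (simulated 27.6%).
- μ = 2, c = 0.7: variance 3.58, SE 0.292, z = 2.05, about 54% (simulated 51.7%).

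Over both values of k, the simulation (2,000 trials per setting) gives 14.6-51.7%. Separate runs with 45 per arm and k = 0.7 give 14-53% and 17-56%. In those runs the pattern of LA significant and OA not, which invites a false claim for LA, occurs in about 12-25% of trials. With c = 1 the paired test rejects in 4.0-6.2%.

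**2. Between-arm test, same conditions.** The expected difference in change is −μ(1−c) + μ(1−c) = 0, so the shift cancels. The two-sample t-test on change rejects in 4.2-5.8% for c = 0.7 or 0.8.

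**3. Efficiency, true LA/OA rate ratio 0.6, no common shift.** For the t-test on change the expected difference is 0.4μ. With k = 0.5:
- μ = 1: variances 1.68 and 2.00, SE = √(3.68/42) = 0.296, z = 1.35, power about 27% (simulated 26.5%).
- μ = 2: variances 3.52 and 4.00, SE = √(7.52/42) = 0.423, z = 1.89, power about 47% (simulated 46.0%).

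| Between-arm analysis | Power |
|---|---|
| t-test on change, 42 per arm | 27-46% |
| Quasi-Poisson, unadjusted, 42 per arm | 33-58% |
| Quasi-Poisson with log(prior count + 1), 42 per arm | 41-67% |
| t-test on change, 45 per arm | 28-48% |
| Negative binomial with log(prior count + 0.5), 45 per arm | 43-70% |

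With no effect, the adjusted quasi-Poisson model rejects in 4.0-5.2% of trials and the negative binomial in 5.0-7.5%. Monte Carlo standard errors are about 1 to 2 percentage points.

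**The case against.** A reader might infer that the exacerbation outcome is planned as an uncontrolled before-after study. The documents do not support that. Section 9 states a between-group aim, and Patients and Eligibility presents the year-before comparison as something done in addition to registering the events. Change from the prior year compared between arms is a fair reading and would be valid. What stands is that the tests named contradict that aim, and the outcome line does nothing to resolve the contradiction.

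A reader might also infer that events are known to be counted more closely in the trial year. The monthly contact is stated for another purpose: "Compliance with the treatment will be evaluated by monthly contact with the study coordinator of respective centre". No text says exacerbations are collected then, and no method is given for either year. Unequal counting is a possibility, not a fact of the plan.

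Season and regression to the mean are weak explanations here. The Protocol says "The treatment will last 12 months, starting and ending at time of the yearly check up of the patients", so both periods span a full year and ordinary seasonality largely cancels. Eligibility does not select on recent exacerbations, so no group-level regression is expected from it.

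It is also fair to say that the false-positive figures come from the assumed shift; without one, the paired test keeps its level. Once the comparison is between arms, the choice between a count model and a t-test on change concerns efficiency, not validity. And the wrong test type affects every secondary and explanatory outcome. Correcting it generally would restore validity here, but would still leave a skewed count analysed as a change score with no provision for unequal follow-up.

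**Conclusion.** The point holds in this form: the comparator and the named tests together specify a within-patient analysis, in conflict with the stated between-group aim, and no between-arm count analysis using the prior-year count is planned. If followed as named, a common fall of 20-30% with no LA effect makes the within-LA test significant in roughly 15-55% of trials, against about 5% with no shift or between arms. If read charitably, the analysis is valid but gives 27-48% power for a rate ratio of 0.6, where an adjusted count model gives about 41-70%.

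The sizes rest on assumed rates of 1 to 2 per year, assumed overdispersion, assumed shifts and complete follow-up. The contradiction itself rests on the text alone. The change should be made, although this is a secondary outcome for which the trial was not sized.

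**What to change.** - Define the outcome as the number of pulmonary exacerbations during the 12 treatment months, with one written definition of an exacerbation and the same source of information for both years.
- Compare arms with a negative binomial or quasi-Poisson model, with the log prior-year count (plus a small constant) as covariate and log follow-up time as offset, so that children who withdraw contribute the time observed. Report the LA/OA rate ratio with its 95% CI.
- List the infectious parameters intended. Compare the continuous ones between arms at 12 months by ANCOVA on the baseline value; the routine blood tests are already scheduled at the start and end of treatment.
- Keep the comparison with the year before as description only, by arm.

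The analysis change needs SAP wording only, since the prior-year comparison is already planned; the definition and source belong in the Protocol or its data-collection instructions. The downsides are modest. A rate ratio is less familiar than a mean change, and the negative binomial error rate can run slightly above nominal at this size (5.0-7.5% in the simulations, against about 4-5% for quasi-Poisson).
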